## 6 Analysis Populations

The analysis populations will consist of participants as defined below:

- The modified intent-to-treat (mITT) population includes all randomized participants who received at least 1 administration of study treatment, and have a baseline MADRS total score and at least 1 postbaseline assessment for the MADRS total score during the double-blind treatment period. Participants will be summarized according to the randomized study treatment.
- The safety population includes all participants who received  $\geq 1$  administration of study treatment. Participants will be summarized according to the study treatment they actually received.

## 7 Patient Disposition

The number and percentage of participants in Safety and mITT Populations will be summarized by treatment group and study center; the number of participants screened will be summarized overall only by study center.

Screen-failure participants (ie, participants screened but not randomized) and the associated reasons for failure to randomize will be tabulated overall for the all screened participants. The number and percentage of participants who enter the double-blind treatment period, complete the double-blind treatment period and of participants who prematurely discontinue during the same period will be presented for each treatment group and pooled across treatment groups. A participant is considered to have completed the study if he/she has completed the double-blind treatment period of the study. The reasons for premature discontinuation from the double-blind treatment period as recorded on the termination pages of the electronic case report forms will be summarized (number and percentage) by treatment group. The percentage is relevant to the total number of randomized participants. Similar disposition information to the double-blind treatment period will be presented for the safety follow-up period. All randomized participants who prematurely discontinue during the double-blind treatment period or the safety follow-up period will be listed by discontinuation reason.

## 8 Demographic and Other Baseline Characteristics

Demographic parameters (age; age group (<20, 20-29, 30-39, 40-49, 50-59, and  $\geq 60$ ); race; ethnicity; sex), baseline characteristics (weight; height; and body mass index, calculated as  $\text{weight [kg]/(height [m])}^2$ ) will be summarized descriptively by treatment group for the Safety and

mITT populations. Continuous variables will be summarized by number of participants and mean, SD, median, minimum, and maximum values. Categorical variables will be summarized by number and percentage of participants.

Medical and surgical history, psychiatric history, non-drug psychiatric treatment history, and other psychiatric history will also be summarized by double-blind treatment group for the Safety Population.

Prior medication is defined as any medication taken before the first dose of double-blind study treatment. Concomitant medication is defined as any medication taken on or after the date of the first dose of the double-blind study treatment. Any medications started after the last visit of double-blind treatment period will not be summarized but will be included in listings.

Both prior and concomitant medication use will be summarized by the number and proportion of participants in each treatment group receiving each medication within each therapeutic class for the double-blind treatment period for the Safety Population. If a participant took a specific medication multiple times or took multiple medications within a specific therapeutic class, that participant would be counted only once for the coded drug name or therapeutic class. Any prior and concomitant medications will be included in listings.

The World Health Organization (WHO) Drug Dictionary Enhanced, March 2017 or newer, will be used to classify prior and concomitant medications by therapeutic class and drug name.

The number and percentage of participants with important protocol deviations will be summarized by treatment group for randomized participants. Deviations related to the following categories will be included:

- Inclusion or exclusion criteria
- Withdrawal criteria
- Treatment or dose
- Concomitant medications

These and any additional important protocol deviations will be reviewed and documented before database lock and unblinding of treatment codes.

## **9 Extent of Exposure and Treatment Compliance**

### **9.1 Extent of Exposure**

The number and percent of participants who received 1, 2, and 3 double-blind study treatment (tablet) will be summarized by treatment group for the Safety Population.

### **9.2 Measurement of Treatment Compliance**

Dosing compliance for double-blind study medication for a specified period is defined as the total number of double-blind study medications actually taken by a participant during that period divided by the number of double-blind study medications that were expected to be taken during the same period multiplied by 100. Descriptive statistics for double-blind study medication dosing compliance will be presented by treatment group for each week, as well as for the whole double-blind treatment period of the study for the Safety Population.

Dosing compliance for placebo tablet during a specified period is defined as the doses actually taken by a participant during that period divided by the doses expected to be taken during the same period multiplied by 100. Descriptive statistics for placebo dose compliance during the double-blind treatment period will be presented by treatment group for the Safety Population.

## **10 Efficacy Analyses**

The efficacy analyses will be based on the mITT population. The last-observation-carried-forward (LOCF) approach will be used to impute missing postbaseline values. Baseline for efficacy is defined as the last nonmissing efficacy assessment before the first dose of study treatment. All statistical tests will be 2-sided hypothesis tests performed at the 5% level of significance for main effects. All confidence intervals will be 2-sided 95% confidence intervals, unless stated otherwise.

For efficacy analyses in which study center is a factor, a small center will be defined as a center with fewer than 5 participants in the mITT Population. All the small centers will be pooled to form a pseudo-center. If the pseudo-center is still a small center, it will be pooled with the smallest non-small center. If there is more than one smallest non-small center, the small pseudo-center will be pooled with the smallest non-small center that has the largest center number.

The rater-administered MADRS will be used for the efficacy analyses.

## 10.1 Primary and Key Secondary Efficacy Endpoints

Primary efficacy endpoint:

- Change from baseline in MADRS total score at 1 day after first dose

Key secondary efficacy endpoint:

- Change from baseline in MADRS total score at Week 3

[figure not shown]
The primary analysis for the primary and key secondary endpoints will be performed using a mixed-effects model for repeated measures (MMRM) with treatment group, visit, pooled study center, and treatment group-by-visit interaction as fixed effects and the baseline value and baseline value-by-visit as covariates. An unstructured covariance matrix will be used to model the covariance of within-participant scores. The Kenward-Roger approximation will be used to estimate denominator degrees of freedom (Kenward and Roger 1997). These analyses will be performed based on all postbaseline scores using only the OCs without imputation of missing values.

In addition, a sensitivity analysis using the LOCF approach will be performed on the primary efficacy and key secondary parameters. The between-treatment group comparisons will be performed by means of an analysis-of-covariance (ANCOVA) model with treatment group and study center as factors and the baseline MADRS total score as the covariate. The LOCF approach will be used to impute missing postbaseline values, provided that at least 1 postbaseline assessment is available. Missing values between the baseline and the first nonmissing postbaseline will be imputed with the baseline value. If all the postbaseline values are missing, the baseline value will not be carried forward. Only the total score of a parameter will be imputed using the LOCF approach; individual item scores will not be carried forward.

## 10.2 Multiple Comparisons Procedure

Let H11, H21, H31, H41 represent the comparisons of AGN-241751 0.25 mg, 1 mg, 3 mg, and 10 mg, respectively with placebo in regarding to the primary efficacy parameter; and let H12, H22, H32, and H42 represent the comparisons of AGN-241751 0.25 mg, 1 mg, 3 mg, and 10 mg, respectively with placebo in regarding to the key secondary efficacy parameter, the graphical procedure as displayed in Figure 10-1 will be employed to control the overall familywise error rate (FWER) at  $\alpha = 0.05$ . The  $\epsilon$  in the figure represents a small positive number less than 0.0001.

**Figure 10-1 Graphical Procedure for Primary and Key Secondary Hypotheses**

### 10.3 Additional Efficacy Endpoints

Additional efficacy endpoints:

- Change from baseline in MADRS total score at 7 days after first dose of treatment
- Change from baseline in Clinical Global Impressions-Severity (CGI-S) at 1 day and 7 days after first dose of double-blind study treatment, and end of double-blind study treatment period (end of Week 3)
- Rate of MADRS sustained responders during treatment
- Rate of MADRS and CGI-S responders at 1 day and 7 days after first dose of double-blind study treatment, and end of double-blind study treatment period (end of Week 3)
- Rate of MADRS sustained remitters during treatment
- Rate of MADRS remitters at 1 day and 7 days after first dose of double-blind study treatment, and end of double-blind study treatment period (end of Week 3)
- Time to first response
- Time to first sustained response
- Time to first remission
- Time to first sustained remission

CGI-S responder is defined as patients achieving a score of  $\leq 2$  on the CGI-S of Illness scale.

During the randomized treatment period, 4 types of events for MADRS total score will be defined based on the following criteria:

- Responder:  $\geq 50\%$  reduction from baseline MADRS total score
- Sustained responder: meet responder criteria at  $\geq 2$  consecutive visits and continued through to final assessment
- Remitter: MADRS total score  $\leq 10$
- Sustained remitter: meet remitter criteria at  $\geq 2$  consecutive visits and continued through to final assessment

MADRS total score is the sum of the 10 items from the MADRS. If more than 2 items of MADRS are missing, then the total score will be set to missing.

Additional quantitative efficacy parameters will be analyzed in the following way:

Analysis of change from baseline in MADRS total score and CGI-S score will be performed using a similar MMRM for the primary and key secondary endpoints. Baseline CGI-S score will be used as a covariate for the analysis of CGI-S score. In addition, these parameters will be analyzed using ANCOVA (with LOCF imputation) as used for the analysis of primary efficacy parameters.

Additional categorical efficacy parameters will be analyzed in the following way:

Rates for categorical parameters (response and remission) will be reported by treatment group and by visit; logistic regression model (with LOCF imputation) will be used to model the probability of a response or the probability of a remission as a function of a treatment group and the corresponding baseline score as explanatory variables.

Additional time to event efficacy parameters will be analyzed in the following way:

For the time to event type of endpoints, the log-rank test will be performed to compare the treatment arms. Kaplan-Meier curves will be plotted for each treatment arm.

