## 6. Study Population

### 6.1. Inclusion Criteria

Participants are eligible to be included in the study only if all of the following criteria apply:

1. Written informed consent from the participant has been obtained prior to any study-related procedures (as described in [Appendix 3](#)).
2. Male or female participants must be 18 to 65 years of age, inclusive, at the time of signing the informed consent.
3. Meet *Diagnostic and Statistical Manual of Mental Disorders*, 5th Edition (DSM-5) criteria for MDD (based on confirmation from the modified Structured Clinical Interview for DSM disorders [SCID]), with a current major depressive episode of at least 8 weeks and not exceeding 18 months in duration at Visit 1.
4. Have a minimum score of 26 on the rater-administered MADRS and a minimum score of 24 on the computer-administered MADRS at both Visit 1 (Screening) and Visit 2 (Baseline).
5. Have a difference of no greater than 7 points between the rater-administered MADRS and computer-administered MADRS at both Visit 1 (Screening) and Visit 2 (Baseline).
6. Have a CGI-S score  $\geq 4$  at both Visit 1 (Screening) and Visit 2 (Baseline).
7. Have a negative serum  $\beta$ -human chorionic gonadotropin ( $\beta$ -hCG) pregnancy test if a woman of childbearing potential (WOCBP).
8. Female participants willing to minimize the risk of becoming pregnancy for the duration of the clinical study and follow-up period. A female participant is eligible to participate if she is not pregnant, not breastfeeding, and at least one of the following conditions applies:
  - a. Not a WOCBPOR
  - b. A WOCBP who agrees to follow the contraceptive guidance in [Appendix 5](#) during the treatment period and for at least 5 terminal half-lives after the last dose of study treatment.

9. Male participants willing to minimize the risk of inducing pregnancy for the duration of the clinical study and follow-up period. A male participant must agree to use contraception as detailed in [Appendix 5](#) of this protocol during the treatment period and for at least 5 terminal half-lives after the last dose of study treatment and refrain from donating sperm during this period.
10. Able, as assessed by the investigator, and willing to follow study instructions and likely to complete all required study visits.

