  8. Positive result at Visit 1 from the urine drug screen (UDS) test for any prohibited medication. Exception: participants with a positive UDS at Visit 1 for opiates, cannabinoids, or episodic use of benzodiazepines may be allowed in the study provided:

- a. The drug was used for a legitimate medical purpose;
  - b. The drug can be discontinued prior to participation in the study (except for episodic use of benzodiazepines which may be continued); and
  - c. A repeat UDS is negative for these substances prior to enrollment (except for episodic use of benzodiazepines which may be continued)
9. Suicide risk, as determined by meeting any of the following criteria:
- a. A suicide attempt within the past year
  - b. Significant risk, as judged by the investigator, based on the psychiatric interview or information collected in the C-SSRS at Visit 1 (Screening) or Visit 2 (Baseline)
  - c. MADRS Item 10 score  $\geq 5$  at Visit 1 (Screening) or Visit 2 (Baseline) on the MADRS
10. At imminent risk of injuring self or others or causing significant damage to property, as judged by the investigator.
11. Requiring concomitant treatment with any of the prohibited medications, supplements, or herbal products listed in [Appendix 6](#), including any psychotropic drug or any drug with psychotropic activity, except as described in [Section 7.7.2](#).
12. Prior participation in any investigational study of AGN-241751.
13. Initiation or termination of psychotherapy for depression within the 3 months preceding Visit 1, or plans to initiate, terminate, or change such therapy during the course of the study. (Support meetings or counseling [eg, marital counseling] are allowed provided they are no more frequent than weekly and do not have treatment of depression as their objective).
14. Ongoing treatment with phototherapy, or termination of phototherapy within 1 month of Visit 1.
15. Known allergy or sensitivity to the study medication or its components.

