### 9.1.1. The Montgomery-Åsberg Depression Rating Scale

The MADRS ([Montgomery and Åsberg 1979](#)) is a clinician-rated scale ([Appendix 8](#)). The MADRS will be used to assess depressive symptomatology. Participants are rated on 10 items to assess feelings of sadness, lassitude, pessimism, inner tension, suicidality, reduced sleep or appetite, difficulty concentrating, and lack of interest. Each item will be scored on a 7-point scale. A score of 0 indicates the absence of symptoms, and a score of 6 indicates symptoms of maximum severity.

A qualified rater (ie, who meets the training requirements and qualifications set by the rater training vendor [Bracket]) at each investigational center will conduct the MADRS assessment.

**The rater-administered MADRS will be used for the primary and secondary efficacy analyses.** In addition to MADRS administration by a qualified rater, each participant will complete an interactive, computer-administered MADRS interview on the dedicated study device. Data from the computer-administered interview will be compared with data derived from the rater-administered interview on an ongoing basis as part of a remote quality assurance program conducted by an independent vendor appointed by the sponsor.

At each visit with a MADRS assessment, the rater-administered MADRS interview will be audio recorded. The computer-administered interview (conducted by participant alone) will involve a series of probe and follow-up questions with multiple-choice response options. At Visit 1 (Screening), the computer administered MADRS will be conducted prior to the rater-administered MADRS. At all other visits, the rater-administered MADRS will be conducted first. At Visit 1 (Screening) and Visit 2 (Baseline), the MADRS will be administered with a look-back timeframe of 1 week. At all other evaluations, the MADRS will be administered with a look-back timeframe of “since last evaluation”.

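### Does the SAP need a stated rule for totalling a MADRS form with one or two unrated items?

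*SAP*

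**What the plan says.** The only definition of the MADRS total in either document is in SAP 10.3: "MADRS total score is the sum of the 10 items from the MADRS". The next sentence there is "If more than 2 items of MADRS are missing, then the total score will be set to missing". It also has to serve the endpoints in SAP 10.1, which are change at 1 day after the first dose (primary) and at Week 3 (key secondary).

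Two other sentences, both in SAP 10.1, come near the question. The MMRM is run "using only the OCs without imputation of missing values". The paragraph on the LOCF sensitivity analysis ends with "Only the total score of a parameter will be imputed using the LOCF approach; individual item scores will not be carried forward".

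SAP Section 16 has no rule for missing scale items. Protocol 9.1.1 and Appendix 8 give the items and their anchors. Protocol 10.4 leaves procedures for missing data to the SAP. SAP 11.5.1 and 11.5.2 set thresholds of the same form for BPRS+ (total missing if more than 1 of 4 items is missing) and CADSS (more than 4 of 23). Both scales are only summarised descriptively.

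**The concern.** A sum of ten items cannot be formed from eight or nine, yet the threshold implies that such totals are used. Two programmers could follow SAP 10.3 and get different values. One might add the rated items. That gives an unrated item the score 0, which Protocol 9.1.1 reserves for absence of symptoms. Another might prorate.

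Simple addition would understate a post-baseline total and overstate improvement. It could turn a near-miss into a response (a reduction of at least 50%) or a remission (a total of 10 or less). The same total feeds the primary MMRM, so the ambiguity seems to reach the main result.

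There is also a conceivable source of unrated items. For visits after baseline, Protocol 9.1.1 says "At all other evaluations, the MADRS will be administered with a look-back timeframe of" the time since the previous rating. At 4 hours post dose that interval lies within one day, and the reduced-sleep item may be hard to score.

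**Working it through.** **Nothing to reproduce.** The plan states no figure that depends on this rule. The sample size has no power basis (SAP 14), and no rate of missing items is given. The check is how large the effect could be under the least favourable reading, which is adding the rated items.

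**Inputs.** Ten items scored 0 to 6 (Protocol 9.1.1); entry total at least 26 (Protocol 6.1); response and remission cuts (SAP 10.3). Assumptions: items equally severe; m items missing (1 or 2); a share p of participants affected.

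**One form.** Recorded total = T × (10 − m)/10. Prorated total = recorded × 10/(10 − m) = T.

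| True total T | Added, m = 1 | Added, m = 2 | Prorated |
|---|---|---|---|
| 20 | 18 | 16 | 20 |
| 26 | 23.4 | 20.8 | 26 |
| 30 | 27 | 24 | 30 |

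**Response.** With a complete baseline and a true reduction r, the form counts as response if (1 − r) × (10 − m)/10 ≤ 0.5.
- m = 1: r ≥ 1 − 0.5/0.9 = 44.4%.
- m = 2: r ≥ 1 − 0.5/0.8 = 37.5%.

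Take a baseline of 30, so that the cut is 15. With one item missing, only a true total of 16 is misclassified (16 × 0.9 = 14.4, while 17 × 0.9 = 15.3). With two missing, true totals of 16 to 18 are misclassified (18 × 0.8 = 14.4, while 19 × 0.8 = 15.2).

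**Remission.** The true total can be as high as 10/0.9 = 11.1 (m = 1) or 10/0.8 = 12.5 (m = 2). In whole numbers that is 11 with one item missing, and 11 or 12 with two.

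**Between-arm contrast.** If the share p is the same in every arm and unrelated to severity, each post-baseline mean is multiplied by 1 − (m/10)p, and so is the difference between arms.

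| Assumed p | Shrinkage, m = 1 | Shrinkage, m = 2 |
|---|---|---|
| 1% | 0.1% | 0.2% |
| 5% | 0.5% | 1% |
| 10% | 1% | 2% |

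**One arm only.** If two items were missing in just one arm, at T = 26 each affected form loses 5.2 points. The arm mean would move by 0.05, 0.26 or 0.52 points at p = 1%, 5% or 10%. Nothing in the documents suggests such an imbalance, and arms are blinded.

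**How likely an incomplete form is.**
- In Appendix 8 every MADRS item is a 0–6 rating with no option for not assessable. The BPRS+ form in Appendix 10 does print one.
- Trained raters administer the MADRS. Each rating is audio-recorded and compared with a computer-administered interview (Protocol 9.1.1).
- At Visits 1 and 2 each participant must "Have a minimum score of 26 on the rater-administered MADRS" and "Have a difference of no greater than 7 points between the rater-administered MADRS and computer-administered MADRS". Exclusion criterion 9 turns on the "MADRS Item 10 score", and Protocol 8.1 uses the same item as a withdrawal criterion throughout, so item 10 has to be rated.
- The 4-hour point is conjecture about one item at a visit that is neither primary nor key secondary.

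**The case for a change.** The best case for a change is that the sponsor's own threshold anticipates incomplete forms, so the SAP should say how they are scored. Protocol 10.4 gives that job to the SAP, the variable is the primary one, and one sentence before unblinding would remove a later choice. The separate specifications mentioned in SAP 4 are described as covering tables, figures and listings, so they cannot be assumed to hold the derivation. The sentence on not carrying item scores forward does not help either. It describes the LOCF sensitivity analysis, which Protocol Amendment 2 removed and which survives only because the SAP is written to Amendment 1.

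The textual part of this stands: the derivation is not written down. The claim of harm does not. Each unfavourable figure needs a method the SAP never states and a missingness rate the documents never give. The wording on analysis without imputation does not block proration, because in context it concerns observed visit scores in the MMRM. Nor is there one uniquely right repair. Proration fits the threshold but assumes that unrated items resemble rated ones, which is doubtful for a sleep item that cannot be judged the same day. Setting the total to missing is also defensible, but sits less well with a threshold of two.

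**Conclusion.** No change to the plan is needed. This is missing detail of a kind that analysts fill sensibly: faced with eight or nine rated items and a rule that keeps the total, they would prorate or set it to missing. Neither scores an unrated symptom as absent.

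Under simple addition the loss is about 10% of the total per missing item. A few participants close to the response or remission cut could be reclassified. The primary contrast would shrink by at most 2% over the assumed range of 1% to 10% affected participants, and by at most 1% if only one item is missing.

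These sizes rest on equally severe items, a complete baseline form, and missingness that is similar across blinded arms. The conclusion would weaken only if incomplete forms were frequent and unequal between arms, which nothing in the documents suggests. For BPRS+ and CADSS the same gap affects descriptive summaries only.

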#### 10.4.1.2. Primary and Secondary Analyses

The primary analysis for the primary and secondary endpoints will be performed using a MMRM with treatment group, visit, pooled study center, and treatment group-by-visit interaction as fixed effects and the baseline value and baseline value-by-visit as covariates. An unstructured covariance matrix will be used to model the covariance of within-participant scores. If the model fails to converge based on the unstructured covariance matrix, then structures of Heterogenous Toeplitz, Toeplitz, and Compound Symmetry will be applied, in the specified order, until the model converges. The Kenward-Roger approximation will be used to estimate denominator degrees of freedom (Kenward and Roger 1997). These analyses will be performed based on all postbaseline scores using only the OCs without imputation of missing values.

[figure not shown]
In addition, a sensitivity analysis using the multiple imputation (MI) approach under missing not at random (MNAR) assumptions will be performed on the primary and secondary efficacy parameters.

Detailed methods and procedures for the above outlined missing data-derived sensitivity analyses will be documented in the final SAP prior to the study database lock.

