## 16 Data Handling Convention

### 16.1 Visit Time windows

Table 16-1 Efficacy and Safety Analysis Visit Definitions

Derived Visit	Scheduled Visit Daya	Window
Baseline	Day 1 d (visit 2)	Last record on or before Index1 a
4-hour Post Dose	4-hour Post Dose (visit 2a)	4-hour post dose
Day 2	Day 2 (visit 3)	Index1 a +1
Day 5	Day 5 (visit 4)	Days [Index1 a +2, IndexA b -1]
Day 8	Day 8 d (visit 5)	IndexA b
Day 9	Day 9 (visit 6)	Day IndexA b +1
Day 12	Day 12 (visit 7)	Days [IndexA b +2, IndexB c -1]
Day 15	Day 15 d (visit 8)	IndexB c
Week 3	Day 22 (visit 9)	Days [IndexB c +1, day of final double-blind visit or ET Visit occurring after IndexB c +1]
End of double-blind treatment period (end of Week 3)	The last available post-baseline assessment during the double-blind treatment period	
End of safety follow-up period	The last available post-baseline assessment during the safety follow-up period.	

a Index1: Day of first double-blind dose

b IndexA: Day of second double-blind dose, if not received, use Index1 + 7 days

c IndexB: Day of third double-blind dose, if not received, use IndexA + 7 days.

d Study treatment administration in clinic.

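### Response and remission labelled end of Week 3 come from the last available rating, carried forward, for participants without a Week 3 rating

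*SAP*

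**What the plan says.** SAP Section 10.3 has one responder item for both scales (MADRS, CGI-S), which reads in part as follows: "responders at 1 day and 7 days after first dose of double-blind study treatment, and end of double-blind study treatment period (end of Week 3"). The remission item opens "Rate of MADRS remitters at 1 day and 7 days after first dose of double-blind study treatment" and ends at the same third time point. There is no CGI-S remission endpoint.

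Two rows of SAP Table 16-1 (Section 16.1) bear on that third time point:

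- **Week 3**, scheduled at Day 22 (Visit 9). Its window opens the day after IndexB (the third dose, or its imputed date) and closes on the "day of final double-blind visit or ET Visit occurring after" that opening day.
- **End of the double-blind period**, whose label matches the Section 10.3 wording almost exactly. It is "The last available post-baseline assessment during the double-blind treatment period", and no minimum day is set.

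Rates are reported by group and visit, and a "logistic regression model (with LOCF imputation) will be used to model the probability of a response or the probability of a remission", with treatment and baseline score as terms. SAP Section 10 also makes LOCF the general rule for missing post-baseline efficacy values.

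Protocol Section 4 (Amendment 2) places responder and remitter rates at 4 hours and on fixed days up to Day 22. Protocol Section 10.4.1 no longer contains LOCF, and its MMRM for the primary and secondary endpoints is "based on all postbaseline scores using only the OCs without imputation of missing values". Other efficacy endpoints are left to the SAP (Protocol Section 10.4.1.1). The SAP cites Amendment 1 (08 Jun 2018) as the latest amendment, the current protocol is Amendment 2 (01 May 2019), and SAP Section 17 records no changes from the protocol.

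**The concern.** A reader of a Week 3 response rate takes it as status after three weekly doses. Under these rules a participant who leaves in the first week contributes the status on leaving, under a Week 3 heading, and the model treats it as observed.

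Leaving can depend on outcome. Protocol Section 7.8 lets participants leave if their depression worsens or is not controlled, and Section 8.1 requires withdrawal on suicide-related criteria that include a MADRS item. Carried-forward status may therefore differ from what Week 3 would have shown, and the arms may differ in who leaves and when. Filling in a single value also understates uncertainty.

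This is distinct from LOCF in the sensitivity analysis of the primary endpoint. For the continuous scores, SAP Sections 10.1 and 10.3 add LOCF ANCOVA to an observed-case MMRM. For response and remission, the LOCF model is the only one specified, so deleting LOCF from Section 10.1 would leave it in place.

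**Working it through.** **No plan figure to reproduce.** Both documents say the sample size (5 × 50 = 250) is not power-based, and neither gives response, remission or by-arm dropout rates.

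**Who is affected**, tracing cases through Table 16-1 with Index1 = Day 1:

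- *Visit 9 rating present.* The last available rating is the Week 3 rating. No effect.
- *Early-termination rating on Day 6, no second dose.* IndexA = 1 + 7 = Day 8, so the rating belongs to the Day 5 window (Days 3 to 7). The last-available row also reports it as end of Week 3. Reading the endpoint on the Week 3 row would not help while LOCF stays, because LOCF carries the same rating into that row. Both rules have to change.
- *Third dose on Day 15, early-termination rating on Day 17.* The Week 3 window opens on Day 16, so this counts as Week 3 although it is 22 − 17 = 5 days early.
- *No rating after 4 hours.* The mITT definition needs only one post-baseline MADRS, so the 4-hour score qualifies.

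**Size of the shift in one arm.** Let d be the share without a Week 3 rating, pL the response rate at their carried-forward rating, and pT the rate they would have had at Week 3.

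Shift = d × (pL − pT), so its absolute size is at most d.

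Inputs: d = 5% is the protocol's upper expectation for participants missing the Week 2 or 3 dose (Section 10.1.3), used as a proxy. It is 0.05 × 50 = 2.5 participants per arm. The values pL = 5–15%, pT = 30–40% and every other d are assumptions.

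| d | Smallest shift | Largest shift | Bound |
|---|---|---|---|
| 5% | 0.05 × (0.15 − 0.30) = −0.75 points | 0.05 × (0.05 − 0.40) = −1.75 points | 5 points |
| 10% | 0.10 × (−0.15) = −1.5 points | 0.10 × (−0.35) = −3.5 points | 10 points |
| 20% | 0.20 × (−0.15) = −3 points | 0.20 × (−0.35) = −7 points | 20 points |

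One participant in 50 is 2 points. If pL = pT (say both 20%), the shift is zero.

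**Effect on a comparison** (50 per arm, two-sided 5%, pL = 0 assumed):

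- *Equal dropout, true rates 30% and 50%.* The difference becomes (1 − d) × 20 points: 19, 18 and 16 at d = 5%, 10% and 20%. Power falls from 53% to 50%, 47% and 40%.
- *No true difference, dropout 5% against 10%, pT = 20–50%.* The spurious difference is 0.05 × pT = 1.0 to 2.5 points. Type I error is 5.4–6.4%, against 5.0–5.7% with no dropout.
- *The same with dropout 5% against 25%.* The spurious difference is 0.20 × pT = 4 to 10 points, and type I error is 8.8–18.2%.

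Type I error was found by exact enumeration of the pooled two-proportion z-test, as a stand-in for the logistic treatment term.

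**The case against.** The strongest reply is that this is a small matter on exploratory endpoints, mostly explained by a SAP that predates Amendment 2. Every treated participant is to have a Visit 9/early-termination rating that includes MADRS and CGI-S. Table 16-1 already has a Day 22 row, and rates are reported by visit. The protocol expects at most 5% to miss later doses. The graphical procedure covers only the primary and key secondary hypotheses. With equal dropout, much of the shift cancels between arms. Participants who leave because they are doing badly might also have been non-responders at Week 3, which brings pT towards pL.

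All of that limits the size, but it does not remove the point. An early-termination rating records the day of leaving. The SAP does not say that the by-visit rates are observed cases, and the model applies LOCF regardless. The 5% counts missed doses, so missing Day 22 ratings could be more frequent. Amendment 2 fixes the days for these endpoints but names no analysis for them, so aligning the SAP would not by itself supply a replacement model.

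Some stronger readings go beyond the documents:

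- *Week 3 rates generally rest on ratings as early as 4 hours.* That requires every later visit and the early-termination visit to be missed.
- *A missing early status is forced to non-response.* The rule "Missing values between the baseline and the first nonmissing postbaseline will be imputed with the baseline value" is written in SAP Section 10.1 for the LOCF ANCOVA of the primary and key secondary parameters. Section 10.3 does not say that the logistic model inherits it.
- *Dropout of 10% in one arm and none in the other moves the difference by 10 points.* That needs a 100-point gap between carried-forward and true response. The rates assumed above give 1.5 to 3.5 points.
- *The binary analysis breaches the full-adherence estimand.* Protocol Section 10.1 limits that framework to the primary and secondary endpoints.

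**Conclusion.** The concern holds for participants without a Week 3 rating. For them, the SAP reports MADRS response, MADRS remission and CGI-S response at the end of Week 3 from an earlier rating, usually the one taken at early termination, and the only specified model treats that value as observed. This differs from the current protocol, which names Day 22 and has dropped LOCF from its efficacy section. The SAP's statement of no changes is therefore out of date. Since the SAP cites Amendment 1, this does not show a deliberate departure.

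The rates could be biased and their uncertainty understated; the documents do not show that they will be. At the protocol's 5% proxy and the assumed response rates, an arm's rate moves by less than one participant in 50. The shift becomes material only if missingness is well above 5% or clearly unequal between arms. The primary and key secondary MMRM are untouched, and nothing in the documents says that these rates select the dose.

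**What to change.** 1. In SAP Section 10.3, define Week 3 response and remission on the Day 22 visit (the Week 3 row of Table 16-1). Narrow that row so that an early-termination rating shortly after the third-dose day does not count as Week 3.
2. Replace the LOCF logistic model by one of two options:
   - a repeated-measures logistic model on observed data, with treatment, visit, treatment-by-visit and baseline, fitted separately for MADRS response, MADRS remission and CGI-S response; or
   - multiple imputation of the scores under missing at random, to match the MMRM, then classification and pooled logistic fits, with CGI-S imputed separately.

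   The missing-not-at-random imputation in Protocol Section 10.4.1.2 should serve only as a sensitivity analysis. It covers the primary and secondary MADRS parameters and supplies nothing for CGI-S.
3. Relabel the last-available row as the last double-blind assessment, for description only.

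The cost is SAP wording, modest programming and slightly wider confidence intervals.
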